### 6.2.5 Long-term Follow-up

Long-term Follow-up will start at Baseline for enrolled subjects who have been permanently discontinued from belumosudil in Study KD025-208 or in Study KD025-213 where they have not yet had an FFS event. The LTFU will occur after the 28-day Follow-up Visit has been completed for enrolled subjects who were actively dosed with belumosudil at Baseline.

Subjects will have LTFU approximately every 3 months until an FFS event occurs. This LTFU assessment will occur by subjects being contacted by telephone, e-mail, or postal mail to confirm survival status, any initiation of new systemic cGVHD therapies, and relapse of underlying disease. Alternatively, this information may be obtained from the subject's medical records.

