3.7.2 Secondary Efficacy Endpoints

3.7.2.1 Duration of Response (DOR)

DOR will be presented according to 5 methodologies:

- The primary definition of DOR is the time from first documentation of response to the time of first documentation of deterioration from best response (e.g., CR to PR, or PR to LR).
- The secondary definition of DOR is the time from first documentation of response to the time of first documentation of lack of response.
- The tertiary definition of DOR is the time from first documentation of response to the time of initiation of new systemic cGVHD therapy.
- The quaternary definition of DOR is the time from first documentation of response to the time of first documentation of lack of response (as the secondary definition) but with durations summed for multiple response/lack of response episodes.
- The FDA definition of DOR is the time from first documentation of response to the time
 of first documentation of organ-level progression, initiation of a new cGVHD therapy, or
 death from any cause, whichever occurs first

The DOR will be reported for early responders, and statistics will include:

- Kaplan-Meier plots and descriptive statistics of DOR. The censoring rules in Table 2 will be applied
- Landmark analyses: Number and percentage of subjects with response sustained for ≥ 3, ≥ 6, ≥ 9, ≥ 12, ≥ 15, ≥ 18, ≥ 24, ≥ 30, ≥ 36 months

Table 2 Censoring Rules for Duration of Response

DOR	Events	Censoring		
Primary	 Deterioration from best response Initiation of new systemic therapy for cGVHD Death 	 Last documented response assessment If LR or initiation of new systemic therapy happens 		

Kadmon Corporation

Page 15 of 26

Secondary	 Documented LR Initiation of new systemic therapy for cGVHD Death 	immediately after two or more missed response assessments, the event date is set as 24 weeks after last documented response assessment prior this event
Tertiary	 Initiation of new systemic therapy for cGVHD Death 	Last response assessment or long term follow up assessment, whichever is the latest and available
Quaternary	 Documented LR Initiation of new systemic therapy for cGVHD Death With summation of DOR from multiple response episodes 	Same as censoring rules for primary and secondary

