FDA defined	 Documentation of organ-level progression Initiation of a new cGVHD therapy Death 	Last documented response assessment If organ-level progression or initiation of new systemic therapy happens immediately after two or more missed response assessments, the event date is set as 24 weeks after last documented response assessment prior this event

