3.7.2.3 Time to Next Treatment (TTNT)

The TTNT will be measured as the time from first treatment to the time of new systemic cGVHD treatment (which will be defined by clinical team review), censored by last response assessment or long term follow up assessment, whichever is the latest and available. TTNT will be analyzed

Kadmon Corporation

Page 17 of 26

by the Kaplan-Meier survival method as well as the landmark analysis at 6, 12, 18, and 24 months.

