3.7.2.4 Failure-free-survival (FFS)

FFS is defined as the absence of new cGVHD systemic therapy, non-relapse mortality and recurrent malignancy (i.e., underlying disease) and is censored by last response assessment or long term follow up assessment, whichever is the latest and available. Kaplan-Meier plots, descriptive statistics of FFS and landmark FFS at 6, 12, 18, 24, 30 and 36 months will be provided. In addition, analyses for the three components of FFS will also be provided.

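### Four of the five DOR definitions count late new-therapy and death events but censor event-free responders at the last response assessment, so censoring depends on the later outcome

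*SAP*

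**What the plan says.** **Events.** SAP 3.7.2.1, Table 2, lists new cGVHD therapy and death as events in all five DOR rows. No row sets a limit on the time since the last response assessment beyond which they stop counting.

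**Censoring.**
- Primary, secondary and FDA-defined: "Last documented response assessment".
- Quaternary: "Same as censoring rules for primary and secondary".
- Tertiary: "Last response assessment or long term follow up assessment, whichever is the latest and available".

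**24-week rule.** The FDA row reads "If organ-level progression or initiation of new systemic therapy happens immediately after two or more missed response assessments", and the event is then dated 24 weeks after the last response assessment before it. The primary and secondary rows have the same rule, with lack of response in place of organ-level progression. Death is not in the rule. The SAP does not say whether LTFU time, in which no response assessment is scheduled, counts as missed.

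**Other endpoints.** TTNT (SAP 3.7.2.3) is "censored by last response assessment or long term follow up assessment, whichever is the latest and available". FFS (3.7.2.4) "is censored by last response assessment or long term follow up assessment, whichever is the latest and available", and OS (3.7.2.5) uses the same rule.

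**Landmarks.** SAP 3.7.2.1 also plans "Number and percentage of subjects with response sustained for" 3 to 36 months.

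**What LTFU collects.** Under Protocol 6.2.5, contacts about every 3 months serve "to confirm survival status, any initiation of new systemic cGVHD therapies, and relapse of underlying disease". Protocol 6.2.2 and the notes to Appendix A, Table 7, give subjects who enrol already in LTFU these contacts only.

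**The concern.** Kaplan-Meier estimation needs the censoring time to be unrelated to what happens afterwards. These four rows break that condition for any responder who leaves scheduled response assessment while still in response. If nothing further happens, the subject leaves the risk set at the last assessment. If therapy is started or the subject dies in LTFU, the subject is put back in the risk set up to the event.

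The Protocol describes three ways to reach LTFU in response: enrolling directly from LTFU before an FFS event (4.3, criterion 1b), tapering to discontinuation after a sustained response (5.2), and reaching the 2-year treatment limit (3.1).

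The study is descriptive and has no hypothesis test. What is at stake is the durability curve and the landmark table in four of five DOR definitions, mainly at late times, which are what an extension study adds.

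**Working it through.** The documents give no DOR estimate to reproduce, so the check traces the rules and then works an example.

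**1. Two responders, both last assessed in response at month 12**
- No event in LTFU to month 36: censored at month 12.
- Death at month 30: event at month 30, with 18 more months at risk.
- New therapy at month 30 instead: event at month 30 if LTFU time is not missed. If it is missed, the event falls at about month 17.5 (12 months + 24 weeks, about 5.5 months).

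In each case the follow-up used depends on whether an event happened later.

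**2. Direction**
The Kaplan-Meier estimate is S(t) = product of (1 - d/n) over event times, where d is the number of events and n the number at risk. Censoring event-free subjects at last contact leaves every d unchanged and makes n the same or larger. The Table 2 curve is therefore never above that curve, and it falls below once late events occur.

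**3. Worked example (invented counts)**
There are 20 responders. Ten stay on drug in response to month 36. Ten are last assessed at month 12 and followed in LTFU to month 36; four of these start new therapy, at months 18, 24, 30 and 33.

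- Table 2: six are censored at month 12, leaving 14 at risk. 13/14 x 12/13 x 11/12 x 10/11 = 10/14 = 71.4%.
- Event-free subjects censored at last contact: 16/20 = 80%.
- All four events re-dated to month 17.5: (14 - 4)/14 = 10/14 and (20 - 4)/20 = 16/20. The 36-month values do not change.

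Landmark counts out of 20, if taken from the DOR times (Table 2 / last-contact censoring):

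| Landmark | LTFU not missed | LTFU missed, all four re-dated |
|---|---|---|
| >= 18 months | 14 / 20 | 10 / 16 |
| >= 24 months | 13 / 19 | 10 / 16 |
| >= 30 months | 12 / 18 | 10 / 16 |
| >= 36 months | 10 / 16 | 10 / 16 |

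**4. Simulation (every rate assumed)**
Each scenario had 300,000 responders, assessments and contacts every 3 months, and follow-up of 36-60 months. The hazard of new therapy or death was ln2/24 per month on and off drug, so the true median is 24 months and true 36-month DOR is 35%. Loss of response was left out to isolate the rule.

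| Drug stopping per month | Reach LTFU | Table 2 median, no re-dating (months) | Table 2 36-month DOR, no re-dating |
|---|---|---|---|
| 1% | 22% | 22.7 | 31.6% |
| 2% | 37% | 21.9 | 28.5% |
| 3% | 48% | 21.2 | 25.7% |
| 4% | 56% | 20.6 | 23.2% |

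Last-contact censoring gave 23.9-24.0 months and 35.2-35.3% throughout. Applying the re-dating at 3% stopping lowered the Table 2 36-month value from 25.7% to 19.0%.

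**5. Response lost unseen in LTFU (also assumed; 3% stopping, no re-dating)**

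| Median time to unseen loss (months) | True median DOR | Table 2 | Last-contact censoring |
|---|---|---|---|
| 24 | 19.7 | 21.1-21.3 | 23.9-24.1 |
| 12 | 17.7 | 21.1-21.3 | 23.9-24.1 |
| 6 | 15.7 | 21.1-21.3 | 23.9-24.1 |
| 3 | 14.0 | 21.1-21.3 | 23.9-24.1 |

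Here Table 2 overstates true DOR, and last-contact censoring overstates it more. Ending follow-up for everyone 6 months after the last assessment also gave 23.9-24.1.

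**The case against.** **Late events are already handled by the 24-week rule.** A reader might infer from the Events column alone that new therapy is counted at any date without adjustment. That is too strong, because the rule can cap its date. But a re-dated event is still an event, death is not covered, and event-free subjects remain at their last assessment. Re-dating made the Kaplan-Meier bias larger in the simulation.

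**Response is unobserved in LTFU, so follow-up should stop at the last assessment.** This is a fair argument for stopping there for everyone. Table 2 stops there only for subjects who have no later event.

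**Last-contact censoring treats unobserved time as response.** This stands. In every unseen-loss case tested it was further from the truth than Table 2 without re-dating, including the mildest. It cannot simply replace Table 2 as the right answer.

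**Much is already planned.** Tertiary DOR, TTNT, FFS and OS use LTFU contacts symmetrically and are not affected. In LTFU a new run would observe only the tertiary events. What it adds is their combination with loss of response seen on treatment.

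**The 2-year route may be late.** KD025-213 main-cohort dosing began by about August 2019, since the 19 February 2020 cut-off was 6 months after the last subject's first visit. If enrolment here began no earlier than mid-2021 (an assumption), the limit falls near four years of treatment for active main-cohort subjects, mostly beyond the 36-month landmark. Direct LTFU entry and taper remain, in unknown numbers.

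**Conclusion.** The concern holds in this form: in four of five DOR definitions, censoring depends on the later outcome, and the 24-week rule does not cure it. Relative to the same recorded events with event-free subjects censored at last contact, the Kaplan-Meier curve is biased downward. The worked example gives 71% against 80% at 36 months under either reading of the 24-week rule.

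Two stronger readings are not supported:
- **That the study will understate true DOR.** Response lost unseen in LTFU pushes the other way, so the net direction is unknown. The size is unknown too, because the documents do not give the number of responders entering LTFU in response. The simulated figures show mechanism and range only.
- **That the 24-month landmark credits only those LTFU subjects who later fail** (the three behind 13/20 in the example). This needs LTFU time not to count as missed and landmarks to be taken from DOR times. The SAP states neither. If LTFU time counts as missed, the re-dated subjects drop out of the later landmarks and the Kaplan-Meier bias grows.

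The change should be made, but with no hypothesis test at stake it concerns the descriptive durability results only.

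**What to change.** 1. For the four definitions, add an analysis with one end-of-follow-up rule for subjects with and without events, and cover death explicitly. Either end DOR follow-up for all at the last response assessment plus one fixed interval, or keep all events and censor event-free subjects at the later of last response or LTFU assessment, as the tertiary row does. Show it beside the current Table 2 analysis and take the landmark counts from the same DOR times. Which version is primary is the sponsor's choice. The fixed interval ignores later events and can overstate DOR if failure is more frequent off drug.
2. Label any version that uses LTFU time as not observing loss of response in LTFU, and state that it can overstate DOR.
3. Report how many responders entered LTFU still in response.
4. State whether LTFU time without scheduled response assessments counts as missed for the 24-week rule.

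The cost is table wording, one count and one extra run on data already collected. No version recovers response lost unseen in LTFU.

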## Study Design

Study KD025-208 was a Phase 2a, open-label, dose-escalation, safety, tolerability, and activity study of belumosudil in subjects with cGVHD. Approximately 48 subjects were to be enrolled to receive oral belumosudil in 3 cohorts, each cohort consisting of 16 subjects (1:1:1 fashion): belumosudil 200 mg QD (Cohort 1); belumosudil 200 mg BID (Cohort 2); and belumosudil 400 mg QD (Cohort 3). Belumosudil was to be administered in 28-day cycles until disease progression or unacceptable toxicity.

Efficacy assessments included using the criteria of 2014 NIH Consensus Development Project on Clinical Trials in cGVHD response (CR, PR, or lack of response [unchanged, mixed, or progression]), cGVHD severity (clinical-reported) and symptom (subject-reported), and Lee cGVHD Symptom Scale (LSS).

Safety assessments included physical examinations (PEs); vital sign measurements; blood sample collection for hematology and chemistry; urinalysis; electrocardiograms (ECGs); adverse event (AE) assessments; concomitant medication assessments; and pregnancy testing for females of childbearing potential.

A Follow-up Safety Visit occurred 28 days (± 7 days) after the last dose of study drug.

Subjects were contacted approximately every 8 weeks via telephone, email, or postal mail to confirm survival status and the initiation of any anti-cancer treatment or any changes in treatment of cGVHD.

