At 3 months after Baseline and every 3 months thereafter ( $\pm$  14 days), subjects will report to the clinic for the same efficacy and safety assessments and dispensing of belumosudil at Baseline. (Height is only required at Baseline.) The study drug diaries for the past 3 months will be collected, and new study drug diaries dispensed. Any remaining belumosudil will be collected.

Subjects may receive belumosudil on Study KD025-217 for up to an additional 2 years, at the discretion of the Investigator (and with guidance from the medical monitor), beyond what they had received in Study KD025-208 or Study KD025-213, cGVHD progression, or unacceptable toxicity.

Efficacy and safety endpoints are described in Section 6.3 and Section 6.4, respectively.

Subjects will return to the clinic for a 28-day Follow-up Visit at 28 days (± 7 days) after the last dose of study drug. Subjects will have LFTU approximately every 3 months until an FFS event occurs. After the 28-day Follow-up Visit has been completed, subjects will be contacted approximately every 3 months by telephone, e-mail, or postal mail to confirm survival status, any initiation of new systemic cGVHD therapies, and relapse of underlying disease. Alternatively, this information may be obtained from the subject's medical records. The Schedule of Assessments is presented in Appendix A: Schedule of Assessments.

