### 6.2.3 Month 3 Visit and Every 3 Month Visits Thereafter (± 14 days)

Three months ( $\pm$  14 days) after Baseline, subjects will have the following procedures/assessments:

- Collection of any remaining belumosudil from subject
- Dispensing belumosudil medication at the same dose. Doses may be taken at home or in the clinic.
- Collection of study drug diary
- Dispensing new study drug diary
- Clinician-reported Global cGVHD Activity assessment

- Response assessment
- PFT\*
- LSS
- Use of corticosteroid dosage
- Use of other cGVHD therapies
- Symptom-directed PE
- Vital signs
- Weight
- KPS
- Hematology lab testing
- Clinical chemistry lab testing
- 12-lead ECG
- Urine pregnancy test (any positive results will be confirmed with serum testing)
- Use of concomitant medications
- AEs
- \* When performing PFT, the same equipment and tester should be used during the course of the study when possible. The PFTs should be conducted in accordance with study guidelines and the American Thoracic Society/European Respiratory Society standardization of lung function testing.

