2.2 Study Design

KD025-217 is a Phase 2, open-label, extended treatment and follow-up study in subjects with cGVHD who have been previously treated with belumosudil in Study KD025-208 or in Study KD025-213.

Subjects who have signed the Informed Consent Form (ICF) will be enrolled in Study KD025-217 if they have met any of the following conditions:

- Actively receiving belumosudil in Study KD025-208 or in Study KD025-213 (excluding adults in the Companion Study and excluding adolescents enrolled under KD025-213 Amendment 2 [01June 2020])
- Is in long-term follow-up (LFTU) on Study KD025-208 or Study KD025-213. Long-term follow-up will be defined as the period after ending treatment with belumosudil and until an FFS event occurs.
- Adult enrolled in the Companion Study as specified in Study KD025-213 Amendment 2 (01 June 2020) and received at least 6 months of treatment or is in LTFU.

After signing the ICF, at Baseline, subjects will undergo efficacy assessments by Clinician-reported Global cGVHD Activity Assessment, response assessment, pulmonary function tests (PFTs), LSS score, and documentation of corticosteroid dosage and/or other therapies for cGVHD.

Subjects will undergo safety assessments including symptom-directed Physical Exams (PE), vital signs, weight, height, Karnofsky Performance Scale (KPS), hematology and clinical chemistry laboratory testing, pregnancy testing, 12-lead Electrocardiogram (ECG), documenting concomitant medications, and monitoring for Adverse Events (AEs). Subjects will continue on their same dosing regimen they received in Study KD025-208 or Study KD025-213: belumosudil 200 mg QD, 200 mg BID, or 400 mg QD. If the Investigator reduced the subject's dose of belumosudil in either Study KD025-208 or Study KD025-213, the subject will continue to receive that same reduced dose treatment with belumosudil throughout Study KD025-217 or until the AE that led to the temporary dose reduction has resolved, in which case the dose treatment can resume at the original dose at the discretion of the Investigator. Subjects will begiven a study drug diary to record daily dosing. Subjects may be administered the first dose either in the clinic or self-administered at home.

At 3 months after Baseline and every 3 months thereafter (± 14 days), subjects will report to the clinic for the same efficacy and safety assessments and dispensing of belumosudil at Baseline.

Kadmon Corporation

Page 8 of 26

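### The fixed 24-week event date in SAP Table 2 does not fit the 3-month response schedule, and it overwrites recorded start dates of new systemic therapy

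*SAP*

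**What the plan says.** SAP 3.7.2.1 defines DOR in five ways, and Table 2 gives the events and censoring rules for each. For primary and secondary DOR, when lack of response (LR) or new systemic therapy occurs "immediately after two or more missed response assessments", then "the event date is set as 24 weeks after last documented response assessment prior this event". The quaternary definition takes the same rule by cross-reference. The FDA-defined row has its own version: "If organ-level progression or initiation of new systemic therapy happens immediately after two or more missed response assessments", with the same 24 weeks. The rule does not name death, and one missed assessment does not trigger it. The SAP gives no reason for 24 weeks.

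The response schedule is in SAP 2.2: "At 3 months after Baseline and every 3 months thereafter (± 14 days), subjects will report to the clinic". Protocol 3.1, 6.2.3 and Appendix A agree. The 28-day visit and long-term follow-up (LTFU) include no response assessment, but LTFU contacts (Protocol 6.2.5) do ask about "any initiation of new systemic cGVHD therapies, and relapse of underlying disease".

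Three other parts of the SAP bear on the rule. Tertiary DOR and time to next treatment (TTNT, 3.7.2.3) use the therapy start date without a 24-week substitution. Section 3.1.6.2 limits event-date imputation to dates whose day is missing.

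**The concern.** A rule for events found after a gap should give a date that makes sense on the visit schedule and should not replace a date that is known. This rule does neither. Its date precedes the second visit whose absence triggers it, so a longer gap can give a shorter DOR. It also replaces a recorded therapy start, so one start can carry two dates in the same report: the true one in tertiary DOR and TTNT, and week 24 in the other four DOR definitions. The Kaplan-Meier estimates of DOR and the percentages with sustained response at the 3-monthly landmarks are at stake.

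**Working it through.** **Inputs.** Assessment interval L = 3 months = 3 × 365.25/12 = 91.3 days = 13.04 weeks (SAP 2.2; Protocol 6.2.3). Visit window ±14 days. Rule date 24 weeks = 168 days = 168/30.44 = 5.52 months (SAP Table 2). Trigger: two or more misses.

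**Can 24 weeks be reproduced?** With L = 13.04 weeks, the second missed visit is due at 2L = 26.1 weeks and the next visit at 3L = 39.1 weeks. Neither is 24. A 12-week interval would put the second missed visit at 2 × 12 = 24 weeks, and an 8-week interval would put the next visit at 3 × 8 = 24 weeks. The documents state neither interval for response assessments.

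**Dates under the rule.** An event first seen after k missed visits is seen at (k + 1)L after the last documented assessment. The SAP replaces this with 24 weeks when k ≥ 2.

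| Missed visits | Seen at (weeks) | Dated by the SAP (weeks) | Difference (weeks) |
|---|---|---|---|
| 0 | 13.0 | 13.0 | 0 |
| 1 | 26.1 | 26.1 | 0 |
| 2 | 39.1 | 24.0 | −15.1 |
| 3 | 52.2 | 24.0 | −28.2 |

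At nominal timing, two misses give a DOR 26.1 − 24.0 = 2.1 weeks shorter than one miss.

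**Visit windows.** With ±14 days at both ends, the one-miss gap is 182.6 ± 28 days, or 22.1 to 30.1 weeks. If visit dates are independent and uniform within their windows (an assumption), the gap exceeds 168 days with probability 1 − (28 − 14.625)²/(2 × 28²) = 1 − 178.9/1568 = 0.886. In the other 11% or so, the one-miss event is not the later one. If 3 months is programmed as 12 weeks, the two dates tie nominally at 24.

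**New therapy.** A start between the second missed visit and the next visit (26.1 to 39.1 weeks) is moved to week 24. That is 26.1 − 24 = 2.1 to 39.1 − 24 = 15.1 weeks early.

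**Landmarks.** Suppose the last documented response is at 3 months of DOR. One miss gives 3 + 6.0 = 9.0 months and meets the 9-month landmark. Two misses give 3 + 5.52 = 8.52 months and do not. The same happens with the last documented response at 0, 6, 9 or 12 months: 5.5, 11.5, 14.5 or 17.5 months against 6, 12, 15 or 18.

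**The case against.** The best defence is that early dating is conservative, in the spirit of SAP 3.1.6.2. For LR this largely stands. LR first seen at week 39.1 arose at an unknown time after the last documented response. Week 24 lies inside that interval and past its midpoint (39.1/2 = 19.6). A reader might infer that LR is misdated by 15 weeks, but that is only the distance to documentation, not a measured error. The defence does not cover a recorded therapy start, whose date is known.

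The reversal between one and two misses is small and depends on visit timing, so it should not be read as universal. The landmark effect needs the last documented response to lie at or near a 3-month multiple of DOR. The 6-month case further requires the first response to be the last assessment before the gap, which is likely to be uncommon among subjects already treated in a parent study.

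Tertiary DOR, TTNT and failure-free survival carry no 24-week rule, so unaltered analyses of therapy start already exist. That limits the harm but leaves the other four definitions as they are.

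Two stronger readings are tempting. One is that the rule dates events too late in parent-study time, because for KD025-208 "Belumosudil was to be administered in 28-day cycles until disease progression or unacceptable toxicity". That sentence gives dosing cycles. The documents do not give the parent response-assessment interval, and 24 weeks would fit an 8-week one. The other is that every therapy start late in LTFU is pulled back to week 24. That follows only if unscheduled assessments count as missed, which the SAP does not say. It is an ambiguity to close, not a demonstrated error.

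**Conclusion.** The rule needs correcting in four of the five DOR definitions, with modest impact. On the 3-month schedule its date falls about 2 weeks before the second missed visit is due, and at nominal timing it places a two-miss event before a one-miss event. The firmer fault is the overwriting of known therapy starts, by 2 to 15 weeks for starts between weeks 26 and 39. This conflicts with tertiary DOR and TTNT, and with the SAP's own limit on imputing event dates.

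The figures assume calendar 3-month visits and gaps that fall within KD025-217. The number of subjects affected is not given. The study has no formal hypothesis or power calculation (Protocol 9.1 and 9.2), so the effect is confined to descriptive DOR curves and landmark percentages.

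**What to change.** Amend SAP Table 2 as follows:

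- Keep the recorded start date of new systemic therapy in every DOR definition.
- For LR or organ-level progression first seen after two or more missed assessments, replace the fixed 24 weeks with the scheduled date of the last missed assessment under the schedule then in force. In KD025-217 this is about 26 weeks for two misses and 39 for three.
- State that periods with no scheduled response assessment, such as LTFU, do not count as missed.

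A two-miss LR then moves by 26.1 − 24.0 = 2.1 weeks, and a three-miss LR by 39.1 − 24.0 = 15.1 weeks. The nominal dates for zero to three misses become 13.0, 26.1, 26.1 and 39.1 weeks, so a longer gap no longer gives an earlier date. This is not guaranteed for every subject, because a one-miss visit attended late in its window can still fall after the scheduled date used for two misses.

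The cost is SAP wording and one derivation, with no new data. DOR becomes slightly less conservative for a few subjects. A sensitivity analysis that censors these subjects at the last documented response assessment is optional.
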